# 11.2.1 Follow-up of reportable abnormal laboratory values

Abnormal laboratory values noted during the infusion visit that require immediate medical intervention will be managed by the study team at the NIH CC, and followed until resolution.

Abnormal laboratory values that do not require immediate medical intervention, but that will be recorded and reported based on the criteria listed in Section 11.2, will be followed until resolution. Laboratory values that remain within the reportable range at the final (4-hour) time point on the day of the infusion visit, will be repeated on an outpatient basis at the NIH CC, until they have returned to the non-reportable range. The first outpatient follow-up blood draw will be scheduled within 72 hours of discharge from the Day Hospital. In the unlikely event that

subsequent follow-up blood draws are necessary, the follow-up intervals will be at the discretion of the Principal Investigator.

# 11.3 Investigator Assessment of Adverse Events

The investigator will assess all AEs with respect to seriousness (criteria listed above), severity (intensity or grade), and causality (relationship to study agent and relationship to research) according to the following guidelines.

# 11.3.1 Severity

The Investigator will grade the severity of each AE according to the "Common Terminology Criteria for Adverse Events (CTCAE)" (v 4.0) which can be found at: http://ctep.cancer.gov/protocolDevelopment/electronic\_applications/ctc.htm

# 11.3.2 Causality

Causality (likelihood that the event is caused by the study agent(s)) will be assessed considering the factors listed under the following categories:

# **Definitely Related**

- reasonable temporal relationship
- follows a known response pattern
- clear evidence to suggest a causal relationship
- there is no alternative etiology

#### **Probably Related**

- reasonable temporal relationship
- follows a suspected response pattern (based on similar agents)
- no evidence of a more likely alternative etiology

#### **Possibly Related**

- reasonable temporal relationship
- little evidence for a more likely alternative etiology

#### Unlikely Related

• does not have a reasonable temporal relationship

OR

• good evidence for a more likely alternative etiology

#### Not Related

• does not have a temporal relationship

OR

• definitely due to an alternative etiology

Note: Other factors should also be considered for each causality category when appropriate. Causality assessment is based on available information at the time of the assessment of the AE. The investigator may revise the causality assessment as additional information becomes available.

# **11.4 Investigator Reporting Responsibilities to the Sponsor**

#### 11.4.1 Adverse Events

AE data will be submitted to the IND sponsor when requested for periodic safety assessments, review of IND annual reports, review of IND safety reports, and preparation of final study reports.

#### 11.4.2 Serious Adverse Events

All SAEs (regardless of relationship and whether or not they are also UPs) must be reported on the Safety Expedited Report Form (SERF) and sent to the Clinical Safety Office (CSO) by fax or e-mail attachment. Deaths and immediately life threatening SAEs must be reported to the CSO within 1 business day after the site becomes aware of the event. All other SAEs must be reported within 3 business days of site awareness.

# **11.4.3 Unanticipated Problems**

UPs that are also AEs must be reported to the CSO by fax or e-mail attachment using the NIH Problem Report Form no later than 7 calendar days of site awareness of the event. UPs that are not AEs are not reported to the CSO.

# 11.5 Sponsor's Reporting Responsibilities

SUSARs, as defined in 21 CFR 312.32 and determined by the IND sponsor, will be reported to FDA and all participating investigators as IND Safety Reports.

The IND sponsor will also submit an IND Annual Report of the progress of the investigation to the FDA as defined in 21 CFR 312.33.

# **11.6 Halting Rules for the Protocol**

Halting the study requires immediate discontinuation of study agent administered for all subjects and suspension of enrollment until a decision is made whether or not to continue enrollment and study agent administration.

The halting rules are:

• 2 or more subjects experience the same or similar SAEs that are possibly, probably, or definitely related to the study agent;

OR

• 2 or more of the same or similar AE in different subjects that are grade 3 or above and are possibly, probably, or definitely related to the study agent;

OR

• any safety issue that the principal investigator and/or the CSO determines should halt the study.

The principal investigator and/or CSO will determine if the study should be halted. In addition, the FDA may halt the study at any time following review of any safety concerns.

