# **11.6.1 Reporting a Study Halt**

If a halting rule is met, a description of the AE(s) or safety issue must be reported by the principal investigator within 1 business day to the CSO and IRB by fax or email.

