#### 11.6.2 Resumption of a Halted Study

The IND sponsor, in collaboration with the principal investigator, will determine if it is safe to resume the study. The principal investigator will notify the IRB of the decision on resumption of the study.

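### Neither counted halting rule in section 11.6 is met by a single related death or immediately life-threatening SAE; a halt then depends on someone choosing it

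*Combined protocol and SAP*

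**What the plan says.** Section 11.6 defines a halt as stopping study agent for all subjects and suspending enrolment until a decision is made on continuing. It lists three rules joined by OR:

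1. "2 or more subjects experience the same or similar SAEs that are possibly, probably, or definitely related to the study agent"
2. "2 or more of the same or similar AE in different subjects that are grade 3 or above", where the events are again at least possibly related to the study agent
3. "any safety issue that the principal investigator and/or the CSO determines should halt the study"

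The section closes with two further sentences: "The principal investigator and/or CSO will determine if the study should be halted", and "the FDA may halt the study at any time following review of any safety concerns".

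What follows a halt is set out next. Under 11.6.1, "If a halting rule is met, a description of the AE(s) or safety issue must be reported by the principal investigator" to the CSO and the IRB within 1 business day. Under 11.6.2 the IND sponsor, working with the principal investigator, "will determine if it is safe to resume the study".

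For the single serious event, 11.4.2 says: "Deaths and immediately life threatening SAEs must be reported to the CSO within 1 business day after the site becomes aware of the event". It attaches no pause to that report.

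**The concern.** The two counted rules rank events in an odd order. Two matching related grade 3 AEs meet a rule fixed in advance. One related death does not, and is left to judgement.

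This matters because the volunteers are healthy and the study offers them no direct benefit (4.4, 8.2). Section 8.1 says that serious effects are not expected, but that statement concerns effects reported in patients with underlying disease. Anaphylaxis is listed separately and without that reassurance, so the protocol itself recognises that one life-threatening reaction could occur. In a study of at most 50 people a second matching event may never occur, or may occur only because dosing went on.

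Meeting a rule also has procedural consequences. It brings the 1-business-day report to the IRB under 11.6.1 and the resumption decision under 11.6.2. Without a halt the IRB hears through Policy 801 (12.1), for which the protocol states no timeline, and the resumption step does not arise.

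**Working it through.** The plan states no operating characteristic for its halting rules, so there is no figure to reproduce. The check has two parts: how each rule treats one event, and how much the gap matters at the planned pace.

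First, apply each provision to k = 1 related death or immediately life-threatening SAE, and then to k = 2 of the same or similar kind in different subjects (graded 3 or above for rule 2).

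| Provision | Requirement | k = 1 | k = 2 |
|---|---|---|---|
| 11.6, rule 1 | at least 2 subjects, same or similar related SAE | 1 < 2, not met | met |
| 11.6, rule 2 | at least 2 matching related AEs of grade 3 or above, different subjects | 1 < 2, not met | met |
| 11.6, rule 3 | a determination by the principal investigator and/or CSO | only if they so determine | same |
| 11.6, FDA | the FDA's own decision after review | only if it so decides | same |
| 11.4.2 | report within 1 business day | report, no pause stated | same |

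So one such event meets no counted rule. Two related deaths from unlike causes might also meet neither, depending on how similarity is read.

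The other supplied text in sections 11.4 to 11.8 contains no single-event trigger. There are two limits on that statement. Part of the text between 11.4.2 and 11.4.3 was not available to this review. Nor was the Safety Review and Communications Plan, which 11.8.1 describes as an internal communications document that also allocates oversight responsibilities.

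Second, pace. The inputs are the accrual period of 60 months, the maximum of 50 volunteers and the initial cohort of 20 (Protocol Summary, sections 3 and 4.1), and the day-5 call with its window of 2 days either way (6.3). Even spacing is assumed.

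- Average interval at the maximum size: 60 months / 50 = 1.2 months.
- Average interval if recruitment stops at 20 and those 20 are spread over the same period: 60 / 20 = 3.0 months.
- Latest planned follow-up contact: 5 + 2 = 7 days after discharge.

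At either average, a report made within 1 business day of site awareness would usually reach the CSO before the next infusion. Averages do not bind the schedule, however. Sections 6.2 and 6.3 set no minimum interval, so a second volunteer could be infused while the first is still within the 7-day follow-up.

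No probability of such an event is calculated. The documents give no rate, and the reading of the rules does not need one.

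**The case against.** The strongest reply is that a listed rule already covers the case. Rule 3 has no count and no grade, and either party can use it alone. A death reaches the sponsor's safety office within 1 business day, so the decision does not rest with the investigator only. A medical monitor is appointed (11.8.2), and deaths also go to the NIAID clinical director (12.2).

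The setting is reassuring too. The drug is widely used. The dose of 250 mg is below the 1 g and 30 mg/kg given to small groups of healthy volunteers without reported serious short-term events (1.4). Prior severe allergy to glucocorticoids is an exclusion (4.3), and vital signs are taken every 30 minutes after infusion (6.2). On this view, an automatic or a judged halt is a design preference.

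Most of this stands, and it limits the size of the point. It does not remove it: power to halt is not a commitment to halt, and none of these reports or checks stops dosing by itself.

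Three stronger readings are tempting but unsupported:

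- A reader might infer that the study could not stop after one death. Rule 3 and the FDA's power show that it could.
- A reader might infer from the closing sentence on who decides that even the counted rules are optional. The text does not settle this. Section 11.6.1 treats a met rule as a halt, and the sentence may refer to rule 3 only. No change to rule 2 need rest on it.
- A reader might take the accrual ceiling of 60 as the number of infusions and conclude that spacing is tighter. Section 4.1 caps volunteers at 50, and section 9 allows for enrolled subjects to be removed after screening.

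**Conclusion.** The point holds as a reading of the supplied text: a single related death or immediately life-threatening SAE triggers a prompt report but meets no counted halting rule, and a halt then rests on discretion. It is an inexpensive improvement to a weak rule, and does not show that the study lacks safety oversight.

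The practical gap is small at an average of 1.2 months between infusions, or longer if recruitment ends at 20. It becomes real if infusions cluster, which the protocol does not prevent.

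The logical finding rests on the text of 11.6 and 11.4.2. The judgement of size rests on even spacing. It would be wrong to assert that no study document provides for a pause, because the Safety Review and Communications Plan and the text between 11.4.2 and 11.4.3 were not seen. If either contains one, 11.6 should say so.

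**What to change.** Add a rule to 11.6: *any one death or immediately life-threatening SAE, life-threatening as defined in 11.1, judged at least possibly related to the study agent under 11.3.2*. Dosing and enrolment are suspended at once, and resumption is decided under 11.6.2.

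State that this rule takes effect without a further determination, and that the principal investigator or the CSO may still halt alone under rule 3. Rules 1 and 2 can stay as they are.

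The cost is a protocol amendment, which needs IRB approval before it is implemented (Statement of Compliance). The downside is a possible short pause after one event, including a recognised risk such as anaphylaxis, until the review under 11.6.2 is done. No extra staff, tests or volunteers are needed.

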# 11 Assessment of Safety

#### **11.1 Definitions**

The NIAID Clinical Safety Office (CSO) is responsible for sponsor safety oversight of this study, and the definitions below comply with CSO requirements.

Adverse Event (AE): An AE is any untoward or unfavorable medical occurrence in a human subject, including any abnormal sign (eg, abnormal physical exam or laboratory finding),

symptom, or disease, temporally associated with the subject's participation in the research, whether or not considered related to the research.

Adverse Reaction (AR): An AE that is caused by an investigational agent (drug or biologic).

**Suspected Adverse Reaction (SAR):** An AE for which there is a reasonable possibility that the investigational agent caused the AE. 'Reasonable possibility' means that there is evidence to suggest a causal relationship between the drug and the AE. An SAR implies a lesser degree of certainty about causality than AR, which implies a high degree of certainty.

Serious Adverse Event (SAE): An SAE is an AE that results in one or more of the following outcomes:

- death
- a life-threatening event (places the subject at immediate risk of death from the event as it occurred)
- an inpatient hospitalization or prolongation of an existing hospitalization
- a persistent or significant incapacity or substantial disruption of the ability to conduct normal life functions
- a congenital anomaly/birth defect
- a medically important event\*

\*Medical and scientific judgment should be exercised in deciding events that may not be immediately life threatening or result in death or hospitalization but may jeopardize the subject or may require intervention to prevent one of the other outcomes listed above.

**Unexpected Adverse Event:** An AE is unexpected if it is not listed in the Investigator's Brochure or Package Insert (for marketed products) or is not listed at the specificity or severity that has been observed. It is the responsibility of the IND sponsor to make this determination.

Serious and Unexpected Suspected Adverse Reaction (SUSAR): A SUSAR is an SAR that is both serious and unexpected.

Unanticipated Problem (UP): A UP is any event, incident, experience, or outcome that is

- 1. unexpected in terms of nature, severity, or frequency in relation to
  - a. the research risks that are described in the IRB-approved research protocol and informed consent document, Investigator's Brochure, or other study documents; and

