# 11.2 Documenting, Recording, and Reporting Adverse Events

AEs occurring from the time the informed consent is signed through study day 5 will be documented, recorded, and reported to the CSO.

The following signs or symptoms are induced by or associated with Methylprednisolone sodium succinate, and any combination of these is expected to occur. These events will not be recorded or reported to the CSO unless they reach a Grade of 3 or higher, are deemed a risk to the participants' rights or well-being, or are deemed appropriate to report under specific circumstances by the Principal Investigator:

- Hyperglycemia
- Leukocytosis
- Neutrophilia
- Monocytopenia
- Eosinopenia
- Flushing
- Increased appetite
- Bitter taste in mouth
- Metallic taste in mouth
- Anxiety

The following signs or symptoms are induced by or associated with Methylprednisolone sodium succinate. These events will not be recorded or reported to the CSO unless they reach a Grade of

4 or higher, are deemed a risk to the participants' rights or well-being, or are deemed appropriate to report under specific circumstances by the Principal Investigator:

• Lymphopenia (Lymphocyte Count Decreased)

The following signs or symptoms are induced by or associated with Methylprednisolone emulsion 1%, and any combination of these is expected to occur. These events will not be recorded or reported to the CSO, unless they reach a Grade of 3 or higher, are deemed a risk to the participants' rights or well-being, or are deemed appropriate to report under specific circumstances by the Principal Investigator:

- Application site burning
- Application site itching
- Application site redness

At each contact with the subject, information regarding AEs will be elicited by appropriate questioning and examinations and will be:

- immediately documented in the subject's medical record/source document,
- recorded in CRIMSON, and
- reported as outlined below (eg, IND sponsor, IRB, and Food and Drug Administration [FDA]).

If a diagnosis is clinically evident (or subsequently determined), the diagnosis rather than the individual signs and symptoms or lab abnormalities will be recorded as the AE.

All abnormal laboratory findings will be reviewed on a routine basis by the principal investigator to identify potential safety signals. An abnormal lab not included on the toxicity table should be assessed in a similar fashion to the criteria above.

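### Section 11.6 does not exempt lymphopenia from its Grade 3 halting rule, while Section 11.2 by default leaves lymphopenia unrecorded and unreported below Grade 4.

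*Combined protocol and SAP*

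**What the plan says.** **Halting (Section 11.6).** The second of three rules is met by "2 or more of the same or similar AE in different subjects that are grade 3 or above", provided the events are at least possibly related to study agent. The other two rules cover similar related serious AEs (SAEs) in two or more subjects, and any safety issue that the principal investigator or the CSO thinks should stop the study. Neither lymphopenia nor the other expected effects of Section 11.2 are exempted.

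**What counts as an AE (Section 11.1).** The definition is broad, "including any abnormal sign (eg, abnormal physical exam or laboratory finding").

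**Recording and reporting (Section 11.2).** Expected effects are listed in three groups. The ten in the first infusion group and the three of the topical emulsion are left out of the record and the CSO reports below Grade 3. Lymphopenia stands alone in its own paragraph. There the default exclusion holds unless the event reaches Grade "4 or higher, are deemed a risk to the participants' rights or well-being", or unless such events "are deemed appropriate to report under specific circumstances by the Principal Investigator".

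**Safeguards.** Section 11.2 also provides: "All abnormal laboratory findings will be reviewed on a routine basis by the principal investigator to identify potential safety signals". Under Section 11.6.1, once a halting rule is met, the events "must be reported by the principal investigator within 1 business day to the CSO and IRB by fax or email". Section 13 has monitors compare CRIMSON data with source documents, including laboratory results.

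**What the sponsor sees (Section 11.4.1).** "AE data will be submitted to the IND sponsor when requested for periodic safety assessments", among other uses.

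**The concern.** The protocol sets two grades for the same event. Section 11.2 treats Grade 3 lymphopenia as an expected drug effect that need not enter the AE record. Section 11.6, read as written, treats two such cases as grounds to stop dosing and enrollment in a trial of healthy volunteers. The text does not say which section governs.

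Two outcomes are possible. The rule may be met by an effect that the sponsor had decided to tolerate, causing an unintended pause. Or the rule may be met without anyone noticing, because the events that satisfy it are not by default in CRIMSON as AEs or in the AE data for periodic sponsor assessments. The CSO shares the halting decision, so the second outcome matters to it as well as to the site.

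**Working it through.** The plan states no operating characteristic for the halting rule, so there is no figure to reproduce. The check is mainly a comparison of text.

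**Step 1: does Grade 3 lymphopenia fall under Section 11.6?**
- It is an abnormal laboratory finding, so Section 11.1 makes it an AE.
- Section 11.3.1 grades AEs by CTCAE v4.0, so a grade is assigned.
- Section 11.3.2 asks, for a possible relation, for plausible timing and little evidence of a likelier cause. For a fall in lymphocytes within hours of an infusion that Section 11.2 says induces or is associated with it, at least a possible relation is the natural call.
- Section 11.6 has no exemption. Two such subjects therefore meet the second rule literally.

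**Step 2: compare recording grade with halting grade for every effect listed in Section 11.2.**

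| Group | Effects | Recorded from | Halting grade | Gap |
|---|---|---|---|---|
| Infusion, first list | 10 | 3 | 3 | 0 |
| Lymphopenia | 1 | 4 | 3 | 4 − 3 = 1 |
| Emulsion | 3 | 3 | 3 | 0 |

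Total: 10 + 1 + 3 = 14 effects. The grades match for 10 + 3 = 13 and differ for 1. Six of the 14 are laboratory effects: hyperglycemia, leukocytosis, neutrophilia, monocytopenia, eosinopenia and lymphopenia. Five of these match and one does not.

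**Step 3: can the event be observed?** Table 2 lists a complete blood count in the post-infusion samples. I assume that a differential is run with it. Section 6.1 names one only at screening, but Section 11.2 could not otherwise cover monocytes and eosinophils.

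**Step 4: how often might the rule be met?** The documents give no rate of Grade 3 lymphopenia. For illustration only, let each subject independently have a related Grade 3 or higher case with assumed probability p. Then

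P(at least 2 of n) = 1 − (1 − p)^n − n·p·(1 − p)^(n−1).

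For n = 20 and p = 0.05: 1 − 0.3585 − 0.3774 ≈ 0.264. Over a range of p, for the initial cohort (20) and the maximum (50):

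| Assumed p | n = 20 | n = 50 |
|---|---|---|
| 0.02 | 0.06 | 0.26 |
| 0.05 | 0.26 | 0.72 |
| 0.10 | 0.61 | 0.97 |
| 0.20 | 0.93 | >0.999 |

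The answer runs from unlikely to near certain, depending wholly on p. The table shows only that the matter cannot be dismissed as remote from what the documents contain.

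**Step 5: where would a Grade 3 case appear?** By default it appears in the laboratory report and the principal investigator's review. It does not appear as an AE in CRIMSON, in CSO reports or in the AE data sent for periodic assessment. Section 11.2.1 ties outpatient repeat draws to values that are recorded and reported under Section 11.2, so a Grade 3 value at the final time point would by default need no repeat.

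**The case against.** The strongest reply is that the sections are compatible. The person who sees every abnormal laboratory result is the person bound to report a met rule within 1 business day. That person may also report lymphopenia below Grade 4 at discretion, and a second related Grade 3 case would be an obvious occasion. This stands: a reader might infer that the sections contradict each other or that the halting rule cannot work for lymphopenia, and the documents do not support either reading. What remains is that nothing requires Grade 3 cases to be counted, and nothing says whether they should be.

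It can also be said that the other 13 effects are little better placed in real time. Section 11.4.1 sends AE data on request, and Sections 11.4.2 and 11.4.3 set deadlines only for SAEs and unanticipated problems. This too stands. Reliance on the principal investigator is not peculiar to lymphopenia. The difference is narrower: a Grade 3 hyperglycemia enters the AE record by default and a Grade 3 lymphopenia does not.

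A reader might further infer that the CSO would not learn of these cases. The documents cannot show that. The Safety Review and Communications Plan (Section 11.8.1) is not among them and may give the CSO laboratory data.

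Finally, the separate paragraph in Section 11.2 looks deliberate, so one could read the specific provision as qualifying the general halting rule. That is plausible, but Section 11.6 does not say so. It supports aligning the text rather than leaving it alone.

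**Conclusion.** The point holds as a low-severity inconsistency in a safety rule. One of 14 listed effects has a recording grade one above the halting grade, and Section 11.6 carries no matching exemption. An expected effect can therefore meet a halting criterion while the qualifying events are by default missing from the AE data.

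The count of 1 in 14 describes the lists, not the risk to subjects. It would be too strong to say that the rule will be met or that a signal will be missed, since no Grade 3 rate is given and the laboratory review is a real safeguard. The consequence is bounded: the principal investigator and/or the CSO decide on a halt, Section 11.6.2 allows the study to resume, and related SAEs and other safety issues have their own rules. Endpoints, analysis and sample size are not affected.

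The conclusion rests on reading Sections 11.1 and 11.6 literally, on a differential being run after infusion, and on nothing in the unseen safety plan already settling the grade.

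**What to change.** Use one grade for lymphopenia in both sections.

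**Default.** Add to the second rule in Section 11.6: *for lymphopenia, grade 4 or above*. This matches the exception already made in Section 11.2, adds no procedures, and leaves the SAE and safety-issue rules in force. Its small downside is a looser trigger for this one effect, chosen without rate data in the documents.

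**Alternative.** If the sponsor's medical monitor wants Grade 3 to count, record and report lymphopenia from Grade 3 in Section 11.2. This costs some extra AE recording. Under Section 11.2.1, Grade 3 values still present at the final time point would also need outpatient repeat draws, the first within 72 hours of discharge.

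Either change is one phrase and needs an IRB-approved amendment. The Safety Review and Communications Plan should be checked for the same grade.
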